**Figure 7 Optional evaluations of Intra-subject Zr-GSK2398852 binding**

Reproducibility of myocardial Zr-GSK2398852 uptake at a specific unlabelled anti-SAP mAb mass dose between different ATTR-CM subjects (vertical lines), and intra-subject dose escalation to confirm Zr-GSK2398852 binding to SAP on amyloid myocardial deposits (horizontal lines).

**10.3.5. Key Elements of Analysis Plan**

Data will be listed and summarized according to the GSK reporting standards, where applicable. Complete details will be documented in the RAP. Any deviations from, or additions to, the original analysis plan described in this protocol will be documented in the RAP and final study report.

The following is planned for the primary endpoints:

Analysis	Study Objective
Endpoints	
 
Assessment of Zr-GSK2398852 cardiac uptake as evaluated by PET imaging at different unlabelled anti-SAP mAb mass doses
 

Analysis (Raw Data)	
 
All data will be listed.
 
Descriptive statistics, where appropriate, will be calculated for all generated PET imaging endpoints over time grouped by total mass.
 

All data up to the time of study completion/withdrawal from study will be included in the analysis, regardless of duration of treatment.

Demographic and baseline characteristics will be summarised.

### 10.3.6. Pharmacokinetics

Plasma concentrations of GSK2398852, which is the total of both  $^{89}\text{Zr}$ -labelled and unlabelled mAb, will be analysed using non-compartmental methods. PK parameters will be summarised by dose with/without treatment period stratification. Dose proportionality will be explored with/without treatment period stratification.

Plasma radioactive concentration - measured by scintillation counter, corrected by radioactivity decay and expressed in molar concentration of the mAb - will be analysed by non-compartmental methods. This radioactive concentration will reflect the total of both labelled-mAb and its metabolites. PK parameters will be summarised by TMD, with/without stratification by treatment period.

The time profile and AUC of the plasma radioactive concentration, resulting from the 10-mg labelled-dose, will be scaled to the TMD and compared to the time profile and AUC of the plasma total mAb concentration.

For each anatomical region defined in the heart, the 3 PET scans will generate 3 values on radioactivity concentration (SUV), and the plasma radio-PK values will function as a marker of plasma clearance. The mechanistic model will probe the combination of tissue SUV and radio-PK as compatible with contributions by a vascular component, a free distribution to interstitium and a component related to tracer bound to amyloid-SAP complexes. The extracted parameters will be summarised for each subject and each mass dose.

### 10.3.7. Evaluation of PET images

The acquired PET information is reconstructed into PET images with due corrections for attenuation, scattered radiation, etc.

The PET images are visually reviewed to identify the general features of body distribution and especially anatomical localization in the heart.

Regions of Interest (RoI) are outlined in the images to define radioactivity distribution. All organ and blood analyses are expressed as SUV (Measured radioactivity concentration corrected for radioactive decay and normalized for administered amount of radioactivity per body weight).

These SUV have a few different definitions depending on organ and selection of interesting tissue components:

#### Local tissue radioactivity concentration in organs in Regions of Interest (RoI)

##### SUVpeak:

A small sphere of 10-12 mm diameter placed in a representative location as seen in the image or transferred from the CT scan. Average of voxel (picture element) values within this volume is calculated.

SUVmean:

A larger outline of the whole organ or representative area or volume as seen in the image or transferred from the CT scan. Average voxel values (picture elements) within this volume is calculated.

Total organ radioactivity amount in Regions of Interest (RoI)SUVtotal\_organ:

An outline of the whole volume of the organ attempting to capture the total amount of radioactivity in that organ, as defined in the PET images or transferred from CT scan. Average of voxel (picture element) values within this volume is calculated.

VOLUMEtotal\_organ:

Corresponding total volume of the organs above

The SUVtotal\_organ and VOLUMEtotal\_organ are used for calculation of fraction of administered dose in that organ.

The organs/tissues of interest for analysis include:

Local tissue radioactivity concentration in organs in Regions of Interest (RoI)

Where relevant and depending on radioactivity uptake pattern:

- A minimum of 5 anatomical positions within the heart (only in the specific heart scans)
- Up to 3 focal and 1 larger location in each of the lungs
- Up to 3 focal and 1 larger location in the liver
- One focal and one large area in spleen
- One focal and one large area in pancreas
- One cortex and one medulla focal area in each of the kidneys
- One large area in the brain
- One large area in one thigh muscle
- Up to 5 small areas of the skin

Other focal or larger areas may be included depending on features in the images

For the regions in the 4\*5 scans focused over the heart, separate and average values will be generated for each of the RoIs.

Total organ radioactivity amount in Regions of Interest (RoI)

- Heart
- Liver
- Spleen
- One lung
- Both kidneys

Other organs may be included depending on features in the images

The PiB studies, performed only across the heart will be evaluated regionally and as “polar maps” using an extracted parameter called “retention index” which indicates the degree of retention as compared to washout.

The WAT studies will be evaluated regionally with automatic software which generates values and “polar maps” representing absolute blood flow values.

Further details on the analysis of the images are given in the Imaging Acquisition and Analysis Manual.

**10.3.7.1. Analysis of PET data**

The tissue SUV and plasma radio-PK values generated will constitute the primary information from the studies. Since plasma radio-PK will be dependent upon time after administration plus mass dose, it will be necessary to relate the tissue SUV to the instant and possibly also to the AUC of the plasma radio-PK.

It is expected that the tissue-to-plasma ratio of the mAb in the heart will be approximately 0.1-0.2 after equilibration between plasma and tissue interstitium. This is guided by an expected plasma space plus interstitium relative space of 0.1-0.2. Within the blood pool of the heart chambers the ratio is expected to be 0.5 (hematocrit about 0.5). We have placed a limit by which the tissue-to-plasma ratio in the cardiac muscle is indicative of entry to the interstitium and binding to amyloid-SAP complexes at 0.5 in balance between a sufficient increase as compared to passive distribution and avoidance of “spill-over” from cardiac blood pools.

More complex models of distribution between plasma and tissue will be explored.

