### 3.2.2. Radiolabelled Anti-SAP mAb: 89Zr-GSK2398852

PET has been selected as the imaging modality for this because it provides sufficiently high spatial resolution (about 6 mm) and a high sensitivity and ability for accurate quantitation of radioactivity concentration throughout the body.

There are several positron emitting radionuclides which are used for human PET studies, but for a study like the one proposed here, the half-life of the radionuclide is a key selection factor. O (2 minutes), C (20 minutes), Ga (68 minutes), and F (2 hours) are frequently used in PET, but these short half-lives would not allow recording of biodistribution of labelled antibodies with plasma elimination half-lives of multiple hours to days and very slow anticipated penetration to the extracellular space. Zr with a half-life of 3.2 days is suited for such studies since it allows a more comprehensive evaluation of tissue biodistribution of the radiolabelled antibody for longer than two days.

A further advantage of Zr is that generic labelling methods have been developed whereby antibodies can be labelled in a standardized procedure and with the binding and

distribution properties retained [Dijkers 2009, Perk 2010, Gaykema 2013, Menke-van der Houven van Oordt CW 2015, Pedit-Taskar 2014, Pedit-Taskar 2015, Laforest 2016].

GSK2398852 (anti-SAP mAb) has been conjugated to Zirconium (Zr) using a non-cleavable linker (See Supplement to Investigator Brochure for GSK2398852 + GSK2315698, GlaxoSmith Kline Document Number 2017N343159\_00).

In vitro experiments have shown that the binding affinity of the Fab domain of Zr-GSK2398852 for SAP is similar to unlabelled anti-SAP mAb which has been therapeutically used in combination with CPHPC in the FIH study (SAP115570). In contrast, the Fc domain of Zr-GSK2398852 has been shown in vitro to have an approximate 30% reduction in C1q binding which could lead to a potential reduction in immunological effector function. Thus the small dose of Zr-GSK2398852 (10 mg) is unlikely to substantially contribute pharmacology whether beneficial or adverse.

The local vascular distribution, tissue permeability, and PK profile of Zr-GSK2398852 in the myocardium of ATTR-CM patients is predicted to be dependent upon five factors:

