## **5.13. Study Overview of Anti-SAP Treatment and $^{89}\text{Zr}$ -GSK2398852**

### **5.13.1. Unlabelled anti-SAP mAb Dose Selection**

The study aims to identify the dose range leading to “optimal”  $^{89}\text{Zr}$ -mAb radiotracer uptake in the heart.

It is anticipated that at very low doses of unlabelled anti-SAP mAb, the clearance of radio-labelled PK may be fast and the expected slow penetration from plasma to heart muscle interstitium may therefore lead to a low uptake of  $^{89}\text{Zr}$ -GSK2398852 in heart tissue. This may give a low radioactivity signal in the heart impairing the possibility to obtain a good measurement.

[figure not shown]
On the other hand, a low unlabelled anti-SAP mAb dose may be beneficial to the binding of  $^{89}\text{Zr}$ -GSK2398852 to amyloid-SAP complexes in the myocardium because of lack of competition with binding of radiolabelled compound from a possible excess of unlabelled mAb within the interstitial space.

At higher TMDs of anti-SAP mAb, the plasma clearance of  $^{89}\text{Zr}$ -GSK2398852 is expected to be slower, facilitating an increased uptake in the tissue interstitium, while at

the same time this may be associated with an increased risk of unlabelled anti-SAP mAb competing with binding of the radiolabelled mAb.

The search for “optimal dose” needs to consider an expected inter-subject variability in the read-out due to biological factors (Figure 4).

**Figure 4** Examples of inter- and intra-subject relationships between tissue / plasma SUV ratio across a range of unlabelled (“cold”) anti-SAP mAb mass doses

In order to increase the probability of obtaining data which provides a good cardiac signal we propose the following concept:

- The first subject in Part A, Dosing Session 1 is investigated with the TMD 80 mg (70 mg unlabelled anti-SAP mAb *plus* 10 mg Zr-GSK2398852). The 80 mg dose is selected because this is the lowest dose in which we have previous adequate human PK data, and these data indicate a terminal elimination half-life in the range of 15 hours. This relatively short plasma residence may hamper the cardiac uptake but is still predicted to have a potential for adequate cardiac signal.
  - The TMD for this subject’s Dosing Session 2 will be determined by the central study team based on data from Dosing Session 1. This will be communicated to the clinical site by filenote prior to Dosing Session 2.

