### **5.13.2. Justification of serial PET scanning per Anti-SAP session**

The time course of the radiolabel mAb PK profile, and the temporal pattern of  $^{89}\text{Zr}$ -GSK2398852 uptake in the myocardium are the two key parameters guiding anti-SAP mAb TMD selection in this PET study.

A total of up to 3 serial  $^{89}\text{Zr}$ -GSK2398852 PET scanning procedures will be performed per dosing session. The scanning times will be predefined only for the first patient, but may be different for the following patients, guided by previous results.

In Part A, the first two subjects will have 3 PET scans per dosing session. The first two scans in these two subjects will be performed over approximately the first 24 hours after  $^{89}\text{Zr}$ -GSK2398852 administration. The third scan will be performed at a later time (timing to be determined from emerging data during the initial part of the study).

After the first two subjects have completed Part A, the subsequent subjects are planned to undergo only two PET scans, the timing of which will be determined by emerging data.

Up to 3 PET scans per dosing session in Part A are justified after administration of  $^{89}\text{Zr}$ -GSK2398852 because the timing of each of these three scanning procedures is a reflection of the predicted time-related whole body biodistribution of  $^{89}\text{Zr}$ -GSK2398852. That is, a later PET scan performed at approximately 72 hours after administration of  $^{89}\text{Zr}$ -GSK2398852 is more likely to detect myocardial tissue specific uptake compared to PET scans performed at earlier time points which are more likely to detect  $^{89}\text{Zr}$ -GSK2398852 within the blood pool of the cardiac chambers.

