### 10.3.3. Inter-Subject Reproducibility of Zr-GSK2398852 Myocardial Uptake

In any one subject in Part A, where the radiolabel PK and cardiac SUV profile of Zr-GSK2398852 is consistent with myocardial uptake during either the 1st or 2nd dosing session (i.e. cardiac / plasma SUV ratio  $\geq 0.5$ ), the reproducibility of this specific unlabelled anti-SAP mAb dose in enabling myocardial uptake of Zr-GSK2398852 may be evaluated by treating further subjects with the same unlabelled anti-SAP mAb mass dose. This is an optional evaluation that is at the discretion of the Investigator or designee in consultation with the Medical Monitor (Figure 7, below).

[figure not shown]

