### 10.3.4. Intra-subject confirmation of Zr-GSK2398852 Myocardial SAP Binding

In any one subject in Part A where the radiolabel PK and cardiac SUV profile of Zr-GSK2398852 is consistent with myocardial uptake during the 1st dosing session (i.e. cardiac / plasma SUV ratio  $\geq 0.5$ ), Zr-GSK2398852 binding to myocardial SAP can be confirmed by performing an *intra*-subject mAb displacement evaluation.

This will be attained by escalating the unlabelled anti-SAP mAb dose in the same subject on their 2nd dosing session (provided the AE profile from the 1st dosing session is acceptable) to evaluate whether a higher unlabelled anti-SAP mAb mass dose can attenuate the cardiac SUV signal compared to their 1st dosing session; this would be indicative of displacement of Zr-GSK2398852 from SAP binding sites on amyloid myocardial deposits.

This is an optional evaluation that is at the discretion of the Investigator or designee in consultation with the Medical Monitor (Figure 7, below).

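### The 0.5 cardiac/plasma limit names no scan time and rests on an equilibrium ratio; near 72 h a heart without binding can pass it, and the displacement check names no plasma normalisation

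*Protocol*

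**What the plan says.** **The limit.** Protocol 10.3.7.1, repeated in SAP 12.4.5, sets 0.5 in cardiac muscle as the tissue-to-plasma ratio indicating entry to the interstitium and binding to amyloid-SAP complexes. The reasoning is that "It is expected that the tissue-to-plasma ratio of the mAb in the heart will be approximately 0.1-0.2 after equilibration between plasma and tissue interstitium", from a plasma-plus-interstitium space of 0.1-0.2, while the chamber blood pool should read 0.5. Protocol 10.3.3 and SAP 7.1.2 use a ratio of at least 0.5 as the ground for testing "the reproducibility of this specific unlabelled anti-SAP mAb dose in enabling myocardial uptake" in further subjects. Protocol 10.3.4 uses it as the entry condition for the displacement check. None of these places names a scan.

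**The expected kinetics.** For a total mass dose of 80 mg, Protocol 5.13.1 says that "these data indicate a terminal elimination half-life in the range of 15 hours". Section 3.2.2 refers to "very slow anticipated penetration to the extracellular space". Section 5.13.2 says that a scan at about 72 h "is more likely to detect myocardial tissue specific uptake compared to PET scans performed at earlier time points". The first subject's third scan is at 72 ± 6 h (5.3.1), and scans may run to about 5 days (3.3.1, 9.6.1).

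**Displacement.** Section 10.3.4 escalates the unlabelled dose in session 2 to "evaluate whether a higher unlabelled anti-SAP mAb mass dose can attenuate the cardiac SUV signal". At higher doses, 5.13.1 says plasma clearance is "expected to be slower, facilitating an increased uptake in the tissue interstitium".

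**Related provisions.** Section 10.3.7.1 says tissue SUV must be related to the instantaneous plasma value and only *possibly* to the AUC. A vascular/free/bound model is planned (10.3.6, SAP 9.1.3) but is tied to neither rule. SAP 9.1.1 lists AUC to the last observation and to infinity, not to each scan.

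**The concern.** The limit is set against an equilibrium value but will be read at a time when the protocol's own figures make equilibrium unlikely. If plasma clears faster than the interstitium empties, the ratio keeps climbing with no binding at all, so 0.5 does not mean the same thing at 24 h and at 72 h.

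The displacement check has the companion problem. Escalating the unlabelled dose is expected to change the plasma curve as well as the binding, so a change in heart signal between sessions mixes the two.

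The 0.5 limit is the only numerical uptake criterion in the documents. It decides whether a mass dose is repeated in further subjects and whether the check that is meant to confirm binding is started. SAP 2.2 records that the PiB and water scans were not done and that CMR data were not databased, so little other evidence is available to correct a wrong reading.

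**Working it through.** **1. The plan's figures.** The ratio is plasma space Vp plus interstitial space Vi times (interstitial/plasma concentration). At equilibrium the concentrations are equal, so the ratio is Vp + Vi = 0.1 to 0.2. The blood pool is 1 − 0.5 = 0.5. Both stated values reproduce.

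**2. No binding, plasma falling.** Take mono-exponential plasma with λ = ln2/half-life, and passive exchange with k = ln2/efflux half-life:

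R(t) = Vp + Vi · k/(k − λ) · [1 − e^(−(k − λ)t)]

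From the documents: half-life 15 h, space Vp + Vi of 0.1-0.2, and the scan times. Assumed: the efflux half-life (scanned over 1-400 h), the split of the space between plasma and interstitium, and that plasma radioactivity has the earlier antibody half-life.

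Example: Vp 0.05, Vi 0.15, efflux half-life 32 h, t = 72 h. Then k = 0.02166, λ = 0.04621, k − λ = −0.02455, and e^(0.02455 × 72) = 5.856. So R = 0.05 + 0.15 × 0.8823 × 4.856 = 0.69.

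Maximum over efflux rates, half-life 15 h:

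| Space (plasma share) | 24 h | 72 h | 120 h |
|---|---|---|---|
| 0.20 (0.05) | 0.25 | 0.69 | 3.21 |
| 0.15 (0) | 0.20 | 0.64 | 3.16 |
| 0.15 (0.05) | 0.19 | 0.48 | 2.16 |
| 0.15 (0.08) | 0.18 | 0.38 | 1.55 |
| 0.10 (0) | 0.14 | 0.43 | 2.11 |

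For space 0.20 with share 0.05, the 72 h ratio reaches 0.5 only for efflux half-lives of about 13 to 90 h. It is 0.30 at 6 h and 0.30 at 200 h. It also stays below 0.5 once the plasma half-life exceeds about 18 h.

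**3. Displacement at 72 h.** Let F be free and B bound tracer, C = e^(−λt), m = k + kb, and binding irreversible:

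- F = Vi·k·(e^(−λt) − e^(−mt))/(m − λ)
- B = kb·Vi·k/(m − λ) · [(1 − e^(−λt))/λ − (1 − e^(−mt))/m]
- SUV is proportional to Vp·C + F + B, and AUC = (1 − e^(−λt))/λ

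One cell: Vp 0.05, Vi 0.15, efflux half-life 24 h, kb 0.03 per h, plasma half-life 15 h in session 1 and an assumed 36 h in session 2.

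| | SUV | SUV/plasma | SUV/AUC |
|---|---|---|---|
| Session 1 | 0.0514 | 1.43 | 0.00247 |
| Session 2, binding unchanged | 0.1111 | 0.44 | 0.00285 |
| Session 2, binding removed | 0.0688 | 0.28 | 0.00176 |

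With all binding removed, raw SUV still rises, by 0.0688/0.0514 = 1.34. With binding unchanged, the tissue/plasma ratio falls to 0.44/1.43 = 0.31 of its session 1 value.

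Grid of 96 cells: two space splits (0.03 + 0.12 and 0.05 + 0.15), efflux half-life 12, 24 or 48 h, kb 0.01, 0.03, 0.1 or 0.3 per h, and session 2 half-life 24, 36, 48 or 60 h.

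| Measure | Falls although binding is unchanged | Does not fall although binding is removed |
|---|---|---|
| Raw SUV | 0 of 96 | 60 of 96 |
| Tissue/plasma ratio | 96 of 96 | 0 of 96 |
| SUV/AUC to scan | 0 of 96 | 15 of 96 |

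These are counts of assumed cells, not probabilities.

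**The case against.** **The passing region is limited.** This stands. It needs an intermediate exchange rate: very fast or very slow exchange keeps the ratio below 0.5. At space 0.15 the answer turns on the plasma share, and at share 0.05 the limit is not passed. The 15 h figure is an earlier antibody half-life, whereas the denominator is radioactivity including metabolites (9.4.2, 10.3.6). It would be wrong to infer that a ratio of 0.5 at 72 h is generally false.

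**Section 10.3.3 speaks of uptake, not binding.** This stands in part. A heart that passes 0.5 by slow washout has taken tracer into the interstitium. But 10.3.7.1 reads the same limit as binding, and 10.3.4 uses it to start the confirmation.

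**Section 10.3.4 names SUV.** This stands. A reader might infer that the plan will declare false displacement, from the 96 of 96 count. That count applies only if a tissue/plasma ratio is used instead, as the caption of Figure 4 might suggest ("relationships between tissue / plasma SUV ratio across a range of unlabelled"); on the literal text the risk is missed displacement. Even that depends on how far clearance slows: 7 of 24 cells at an assumed 24 h, 20 of 24 at 60 h.

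**The imaging centre derives the PET variables (SAP 12.4.4), and its manual is not available here.** This stands. One might infer that no ratio will be derived, or that the planned-time convention in SAP 12.4.3 will mistime it. Absence from the SAP displays does not show the first, and SAP 12.4.3 need not govern the imaging centre. A scan at 72 ± 6 h and a sample at 72 ± 4 h could lie 10 h apart, a factor of 2^(10/15) = 1.59, but only at opposite extremes and without interpolation. The cardiac listing shell also carries blood-pool SUV from the same scan as a reference.

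**Conclusion.** The concern holds in a bounded form. The limit has no scan time, and its justification does not cover the late scan under the half-life and penetration that the protocol expects. At 72 h with a 15 h half-life, a heart without binding can pass 0.5 if the passive space is near 0.2 and exchange is slow but not extremely slow. At space 0.15 the maximum is 0.38-0.64, depending on the plasma share. At space 0.1, and at 24 h for any space in the range, it does not pass. By 120 h every space in the range can. Protocol 3.3.3 says that amyloid raises the extracellular volume, which points towards the upper end.

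For displacement, raw SUV is a weak measure if clearance slows as expected, and the instantaneous ratio fails in the opposite direction. Exchange rate, plasma share, binding rate and the session 2 half-life are all assumptions.

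The study tests no hypothesis and both evaluations are optional, so no error rate is affected. What is at stake is whether uptake is described as binding, and which mass dose is repeated.

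**What to change.** - **Protocol 10.3.7.1 and SAP 12.4.5:** drop the qualifier *possibly*, so that tissue SUV is related to the AUC as well as to the instantaneous plasma value. Derive plasma radio-PK AUC from time 0 to each scan, using actual scan and sample times with plasma interpolated to the scan. Use same-scan blood-pool SUV as a cross-check.
- **Protocol 10.3.3, 10.3.4 and SAP 7.1.2:** apply 0.5 to myocardial-wall regions. At each scan, show beside it the no-binding ratio computed from that session's own plasma curve, over passive space 0.1-0.2 and a stated range of exchange rates. Do not describe a ratio of 0.5 or more as binding when it lies within that range.
- **Protocol 10.3.4:** report wall SUV, tissue/plasma ratio and SUV/AUC at the same nominal scan time in both sessions. Do not treat a fall in the ratio alone as displacement, or an unchanged raw SUV alone as its absence.
- **SAP Listing 33:** add the ratio, its no-binding range and SUV/AUC.

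**Cost:** wording and a few derived variables from data already collected. For noise-free mono-exponential plasma, the Protocol Table 5 sampling times recover AUC to 72 h within 0.4%; a later scan needs extrapolation or one of the additional samples that Table 5 allows. Some true binders would not be called: with a 72 h ceiling of 0.86 (space 0.2, no plasma share, half-life 15 h), 5 of 24 binding cells fall below it. SUV/AUC is only a partial correction: it misses 15 of 96 and drifts up 1.01- to 1.57-fold with binding unchanged. The result should therefore stay descriptive.

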### 3.3.3. Cardiac Magnetic Resonance (CMR) Imaging

CMR methods precisely and specifically quantify the left ventricle (LV) mass and the cardiac ECV, both of which are increased by the presence and extent of cardiac amyloid deposition. Raised ECV values have been shown to be associated with a worse clinical prognosis in ATTR-CM [[Martinez-Naharro 2017](#)].

However, the specificity of ECV as a measure of amyloid involvement in myocardial tissue remains to be determined. In this study, contrast-enhanced CMR will be used to determine the amyloid load and myocardial perfusion in ATTR-CM patients at baseline. Baseline CMR will also enable exploratory investigations to co-localise regions of Zr-GSK2398852 cardiac uptake on PET imaging with anatomical sites of TTR amyloid deposition within the myocardium, as well as potentially loco-regional intramyocardial perfusion parameters since myocardial blood flow is expected to be an important determinant of Zr-GSK2398852 myocardial uptake and distribution.

Whenever possible, the baseline contrast-enhanced CMR should be performed after a subject has passed other eligibility requirements.

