### **9.6.2. Cardiac Magnetic Resonance (CMR) Imaging**

Subjects will be asked to refrain from alcohol, caffeine, and nicotine on the days of CMR exams. Each baseline enhanced CMR imaging session will take approximately 45-60 minutes, with a maximum scan time inside of the scanner of approximately 90 minutes. If a scanning failure occurs, there will be a minimum of 24 hours prior to rescan.

As far as it is practicable, the local study site will use the same CMR imaging sequences, software acquisition, and contrast agent (i.e. DotaremTM) that is currently being used in the Phase 2 trial.

**Whenever possible, the baseline contrast enhanced MRI scan will be performed after a subject has passed other eligibility requirements.**

For each subject, if follow-up CMR examination(s) are clinically indicated for evaluation of potential cardiac adverse event(s) the same scanner as to the one used at the baseline examination should be used wherever feasible. Further details of site training and qualification procedures, and scanning protocols are provided in a dedicated Image Acquisition Manual to ensure consistency across study sites. Additional exploratory CMR endpoints, as detailed in the Imaging Acquisition Guidelines, may also be acquired for exploratory purposes.

All CMR scans will be reviewed at the local study site for disease and potential anti-SAP mAb-related clinical abnormalities.

However, image analysis for key CMR parameters which might be determinant for  $^{89}\text{Zr}$ -GSK2398852 myocardial uptake (e.g. extracellular volume [ECV] and myocardial perfusion) will be performed by a qualified imaging laboratory.

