For the regions in the 4*5 scans focused over the heart, separate and average values will be generated for each of the Rols.

Total organ radioactivity amount in Regions of Interest (RoI)

- Heart
- Liver
- Spleen
- One lung
- Each kidney

Other organs may be included depending on features in the images.

Analysis of PET Data

The tissue SUV and plasma radio-PK values generated will constitute the primary information from the studies. Since plasma radio-PK will be dependent upon time after administration plus mass dose, it will be necessary to relate the tissue SUV to the instant and possibly also to the AUC of the plasma radio-PK.

It is expected that the tissue-to-plasma ratio of the mAb in the heart will be approximately 0.1-0.2 after equilibration between plasma and tissue interstitium. This is guided by an expected plasma

space plus interstitium relative space of 0.1-0.2. Within the blood pool of the heart chambers the ratio is expected to be 0.5 (hematocrit about 0.5).

We have placed a limit by which the tissue-to-plasma ratio in the cardiac muscle is indicative of entry to the interstitium and binding to amyloid-SAP complexes at 0.5 in balance between a sufficient increase as compared to passive distribution and avoidance of “spill-over” from cardiac blood pools.

More complex models of distribution between plasma and tissue may be explored.

Storage and potential further analyses of images

The primary PET and CT images in digital form will be anonymized and stored in an image repository under the control of GSK and may be used for further analyses.

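### The 0.5 cardiac/plasma limit rests on one fixed passive space of 0.1-0.2, with no allowance for the raised extracellular volume of amyloid hearts, and the SAP drops the CMR analysis that could check it

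*Protocol*

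**What the plan says.** Protocol 10.3.7.1 gives the reasoning behind the limit. It expects a heart-to-plasma ratio of 0.1-0.2 once plasma and interstitium have equilibrated, and explains: "This is guided by an expected plasma space plus interstitium relative space of 0.1-0.2". It expects a ratio of 0.5 in the cardiac blood pool. It then places the limit for interstitial entry and "binding to amyloid-SAP complexes at 0.5 in balance between a sufficient increase as compared to passive distribution", while also guarding against spill-over from the chambers. SAP 12.4.5 carries this over: "It is expected that the tissue-to-plasma ratio of the mAb in the heart will be approximately 0.1-0.2 after equilibration between plasma and tissue interstitium".

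The limit has a use. Under Protocol 10.3.3 and 10.3.4 and SAP 7.1.2, a ratio of at least 0.5 counts as consistent with myocardial uptake. It opens the optional reproducibility evaluation and, in the Protocol, the optional displacement evaluation.

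Elsewhere the Protocol describes the space in diseased hearts. Section 3.3.3 says CMR quantifies LV mass and "the cardiac ECV, both of which are increased by the presence and extent of cardiac amyloid deposition". Section 9.6.2 plans laboratory analysis of CMR parameters that might determine tracer uptake: "e.g. extracellular volume [ECV] and myocardial perfusion) will be performed by a qualified imaging laboratory".

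SAP 2.2 withdraws this. It states that the CMR/ECHO analysis will not be done, because CMR was only a baseline safety measure, and that the data were not databased. The same section keeps an informal scatter plot of regional uptake against MRI signal, and it drops the PiB and water PET scans.

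**The concern.** Plasma plus interstitial space is, in ordinary usage, extracellular volume. If a non-binding antibody equilibrates through that space, its tissue-to-plasma ratio approaches the fraction of tissue that the space occupies. A larger space gives a larger ratio without any binding. All eligible subjects have ATTR-CM, and the Protocol says the space grows with amyloid load. The passive ratio would then tend to be highest in the hearts with most amyloid, which are also those where binding is most expected. One cut-off for everyone mixes antibody binding with disease load.

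This would remain at perfect equilibrium, so it is separate from scan timing and from the haematocrit assumed for the blood pool.

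At stake is how a positive reading is described. The PET results will be listings and individual plots from at most six subjects. The stated limit is therefore what a reader will use to decide whether an uptake value means binding.

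**Working it through.** **Inputs from the documents.** Passive space 0.1-0.2, haematocrit about 0.5 and limit 0.5 (Protocol 10.3.7.1; SAP 12.4.5). Direction of ECV in cardiac amyloid: increased, with no size given (Protocol 3.3.3).

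**Assumptions, because the documents give no figure.** CMR ECV stands for plasma plus interstitial space. ECV is varied from 0.3 to 0.7. The share of that space open to the antibody, f, is varied from 0.5 to 1.0.

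**The plan's own figures.** At equilibrium the interstitial and plasma concentrations are equal, so passive ratio = accessible space × 1. A space of 0.1-0.2 gives a ratio of 0.1-0.2, as stated. The blood pool gives 1 − 0.5 = 0.5, as stated. The limit itself is a judgement between two aims and does not come from a formula.

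**Implied margin** = 0.5 / passive ratio: 0.5/0.1 = 5.0 and 0.5/0.2 = 2.5.

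**With an enlarged space.** Passive ratio = f × ECV; margin = 0.5 / (f × ECV). Each cell shows the ratio, then the margin.

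| Assumed ECV | f = 1 | f = 0.75 | f = 0.5 |
|---|---|---|---|
| 0.3 | 0.30; 1.67 | 0.225; 2.22 | 0.15; 3.33 |
| 0.4 | 0.40; 1.25 | 0.30; 1.67 | 0.20; 2.50 |
| 0.5 | 0.50; 1.00 | 0.375; 1.33 | 0.25; 2.00 |
| 0.6 | 0.60; 0.83 | 0.45; 1.11 | 0.30; 1.67 |
| 0.7 | 0.70; 0.71 | 0.525; 0.95 | 0.35; 1.43 |

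**Break-even ECV**, where passive distribution alone reaches the limit, is 0.5/f: 0.50 at full access, 0.67 at 75% and 1.0 at 50%.

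Any accessible space (f × ECV) above 0.2 takes the margin below the smallest value the plan implies. The limit is reached without binding only when accessible space is 0.5 or more.

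**The case against.** The strongest reply is that the documents give a direction and no size. They contain no ECV value for these patients, and they do not say that 0.1-0.2 describes a normal heart. A reader might infer that the limit fails in this population; that is not shown. At assumed ECVs of 0.3 and 0.4 the limit stays above the passive ratio even with full access.

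Access may also be well short of full. Protocol 3.2.2 expects slow penetration to the extracellular space and reduced flow in amyloid areas, and 3.1 notes a continuous cardiac endothelium. This stands. It is why ECV serves only as an upper bound, and why the table varies f.

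A reader might also infer that 0.5 is the only evidence of binding. It is not. Protocol 10.3.6 and SAP 9.1.3 plan a mechanistic model with vascular, free-interstitial and bound components. Protocol 10.3.4 offers an intra-subject displacement test, and 5.12.1.2 relies on within-patient comparison to limit the effect of differing amyloid load. These help, with limits. Displacement is optional, and within-patient comparison needs two sessions, which only Part A has. The model has at most three scan times per session, and two after the first two subjects. Without an outside value for interstitial space, free and bound tracer will be hard to separate. SAP Appendix 9 lists no display of the model's parameters or of the tissue-to-plasma ratio.

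A third tempting reading is that each subject's ECV is already to hand. That is the Protocol's plan only; SAP 2.2 cancels the analysis.

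Finally, the consequence is modest. No hypothesis is tested, the ratio opens only discretionary evaluations, and comparison with ECV changes a call only where ECV is 0.5 or more. One subject-level ECV is also a coarse comparator for focal regions 10-12 mm across. All of this stands and keeps the point to a low-cost improvement. The Protocol's caution about ECV's specificity for amyloid matters less, because here ECV is used as a measure of space.

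**Conclusion.** The point holds in a limited form. The limit is justified against one fixed passive space, the Protocol says that space is enlarged in this disease, and neither document shows that 0.1-0.2 allows for the enlargement or relates the limit to a subject's own ECV. To the extent that 0.1-0.2 describes unenlarged tissue, the true margin is below the implied 2.5- to 5-fold.

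How far below cannot be settled from the documents. Under the assumptions above it could be anything from little changed (2.50 at ECV 0.4 with 50% access) to absent (ECV of 0.5 or more with full access). A ratio of 0.5 therefore supports uptake, but alone it does not exclude passive distribution. The SAP's decision not to analyse CMR removes the planned measurement that would narrow this range.

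**What to change.** Amend SAP 2.2 to retrieve the baseline CMR ECV that Protocol 9.6.2 already plans, for at most six subjects. Reconcile the statement that CMR was a safety measure only with Protocol 3.3.3 and 9.6.2, and with the MRI scatter plot that SAP 2.2 retains.

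In Protocol 10.3.7.1 and SAP 12.4.5, list the cardiac/plasma ratio, ECV and ratio/ECV together, with a matching listing in SAP Appendix 9. State that ECV is treated as an upper bound on antibody-accessible space. Describe a ratio of at least 0.5 that does not exceed the subject's ECV as compatible with passive distribution. A ratio above ECV removes the equilibrium passive explanation, but should still be read with the mechanistic model.

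If ECV cannot be retrieved, add one sentence to both documents: a ratio of at least 0.5 indicates uptake and does not by itself establish binding to amyloid-SAP complexes.

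The cost is a small retrieval step, since the data were not databased, one added listing, and a more cautious call in high-ECV hearts. No new scan is needed.
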